**Table 1. Schedule of Assessments**

Abbreviations used in this table may be found in Appendix 12 .	Scr.	Treatment Period				Gluten Challenge (Day 15 to 28)			Biopsy	FU	ET	Notes
Visit Identifier	V1	V2	V3	V4	V5	V6	V7	V8	V9	ET		
 
Day relative to start of study intervention (Day 1).
 
See Section 8.4.3 for follow-up AE and SAE assessments.
 
D16 and D21 are phone call visits (See Section 8.1.1) for collection of AEs and concomitant medications.
 

Type (Site or Phone Call)	Site	Site	Site	Site	Site	Phone	Phone	Site	Site	Site		
Study Day (D)	Up to -42 days	D1	D4	D7	D15	D16	D21	D29	D42	ET		
Visit Window (days)					+2	±2	+3	+3				
Prior/concomitant meds/procedures, incidental gluten exposure	X	X	X	X	X	X	X	X	X			
 
See Section 6.9 for additional information.
 
Incidental gluten exposure checked daily; entered into eDiary and reviewed at study visits.
 

EGD with biopsy (approx. 6 duodenal biopsies)	X							X		X		
 
EGD should only be performed after the participant has qualified with all other inclusion/exclusion criteria.
 
For rescreening, EGD does not need to be repeated if 1) <3 months have elapsed from last screening assessment, 2) the participant has continued GFD and 3) the participant has not undergone a GC.
 
Only participants who have completed all 3 doses of study intervention and at least 7 days of GC should undergo EGD with biopsy at D29 or at ET visit (if participant discontinues prior to D29).
 

PGIS		X			X			X	X	X		
 
Day 1 PGIS should be completed pre-dose (at least 5 minutes prior to infusion).
 

PGIC					X			X	X	X		
GC					D15-28 daily							
 
GC completed in clinic on D15 and at home for the next 13 days (D16 to D28).
 
Participants who withdraw from treatment and do not receive 3 full doses should not receive GC.
 

CDSD v2.1	To be completed daily											
 
PRO (CDSD® v2.1) will be completed via eDiary for at least 7 consecutive days during screening.
 
For re-screening: CDSD v2.1 only needs to be repeated if >3 months have elapsed from end of last PRO administration.
 

CONFIDENTIAL

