### **8.2.1. Gluten Challenge**

All eligible, enrolled participants that received all three doses of study intervention will undergo a 2-week GC at starting Day 15.

- Participants are required to fast for at least 6 hours (or overnight), except for water and any medications they might have previously been prescribed, prior to GC. This pertains to both the study clinic visit during which the GC is performed (see [SoA](#)) and the at-home GC.
- At the Day 15 study visit, a qualified staff member will prepare the GC.
- Participants will consume 9g of gluten protein PO in the clinic and the participant will be observed for at least 4 hours to monitor for hyperacute reactions requiring medical treatment and collection of biomarker samples.
- Materials will be sent home with the participant to complete the GC daily for the next 13 days.

Completion of the GC is defined as consumption of the entirety of the 9g GC within approximately 15 minutes.

- At the Day 15 visit, participants will consume the GC on site under the observation of site staff. Participants will complete the remaining days of GC at home and document the completion of the GC via the eDiary.

Compliance with the GC is defined as completion of all 14 days of the GC. Only participants fully compliant with the GC may be analyzed as part of the PPS (see [Section 9.3](#)).

Only participants who have completed at least 7 days of GC should undergo the second EGD with biopsy. For participants who:

- Continue in the study, the EGD with biopsy will take place at the Day 29 visit (see [SoA](#)).
- Discontinue early, the EGD with biopsy will take place at the ET visit (see [SoA](#)).

Any symptoms associated with the GC should be recorded as AEs (see [Section 8.4](#)). Any AEs associated with the GC study assessment are separate to AEs related to study intervention (KAN-101/placebo).

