4 16Oct2024	Amendment 1 20Mar2024	Update Appendix 2.1 Added summary and analysis for Nausea Score and Vomiting Frequency and change from baseline	Analysis windows were updated. Sections 2.3 and 5.3.2, CDSD 1-Day, 3-Day, 7-Day Nausea Score and Vomiting Frequency and change from baseline at each timepoint post-gluten challenge will be summarized and analyzed using Wilcoxon Signed-rank test for within treatment paired comparison and Wilcoxon Rank Sum test for comparison between placebo vs each of KAN group.
5 13Dec2024	Amendment 1 20Mar2024	Made clarification for CDSD average calculation. Made clarification for analysis set.	Section 2.3, 5.3.2, Appendix 2.2, CDSD average score calculation was updated. Intent-To-Treat (ITT) was removed from Sections 3, 5.1.2, 5.2.2.

Table 1 Summary of Changes

Version/Date	Associated Protocol Amendment	Rationale	Specific Changes
		
Marsh-Oberhuber score is categorical
 
COVID-19 pandemic is over.
 
Map IL-2 and CDSD data to Day 15 if first GC is on Day 14 or Day 16.
	
Section 5.3.1, Baseline and Day 29 Marsh-Oberhuber score will be summarized with frequency and percentage. Change from baseline to Day 29 will be summarized using shift table
 
Section 5.5, COVID-19 listing and summary were removed
 
Appendix 2.1, Analysis window for IL-2 and CDSD was added (Table 8)

03Feb2025 20Mar2024	Amendment 1	
How to handle CDSD multiple records on a same day
 
Make GC start day window wider
	
Section 5.3.2, added a statement: If there are multiple records on a same day, the earliest one will be used for analysis.
 
Section 5.3.2, added weekly time definition of analysis window for Week 2 and Week 3 when the first GC day is at Day 17.
 
Appendix Table 8, analysis window for first GC day was changed from “Day 14 to Day 16” to “Day 14 to Day 17”.

Table 1 Summary of Changes

Version/Date	Associated Protocol Amendment	Rationale	Specific Changes
		Updated analysis windows for PGIS, PGIC, vital signs, and lab tests.	Appendix 2 Tables 3, 4, 5: analysis windows of Day 15 and Day 29 were updated to relative to the first (or second) GC day instead of absolute study day.

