2.3. Exploratory Endpoints

- Changes from baseline in Marsh-Oberhuber score assessed via EGD with biopsy after 2-week GC.
- The biopsy will be performed at screening and Day 29, or ET visit. Baseline is the last non-missing Marsh-Oberhuber score at screening.
- CSDS

- CDSD is a patient reported outcome (PRO) questionnaire collected daily. The version 2.1 includes 5 severity items and 3 frequency supplement questions (see [Appendix 2.2](#)) that will be collected daily.
 - CDSD Total Score is the sum of all 5 severity items. The CDSD Weekly Average Total Score will be calculated , for details on the calculation see below, Section [5.3.2](#) and [Appendix 2.2](#).
 - The CDSD Gastrointestinal (GI) Domain Score is the sum of items 1-4. The CDSD Weekly Average Gastrointestinal (GI) Domain Score will be calculated, for details on the calculation see below, Section [5.3.2](#) and [Appendix 2.2](#) .
 - For CDSD Nausea score and vomiting frequency, in addition to weekly average score, 3-day average will be derived as well (every 3 days start from Day 15 GC until Day 41). If 2 observations are missing, the 3-day average score will not be calculated. Day 15 Nausea score and vomiting frequency will be analyzed as well.
- For CDSD Total score, GI Domain score, individual severity item and frequency supplement question, the Baseline value is the average of most recent 7-day interval scores before Day 1 (not include Day 1) with at least 4 days with non-missing scores, and will be used as the baseline to calculate the change from baseline to the 1-day, 3-day average and weekly average. If there are ≥ 4 days missing scores in any 7-day interval before Day 1, the baseline value is set as missing.
- For post-baseline weekly average score calculation, Week 1 is from Day 1 to Day 7, Week 2 is from Day 8 to the day before Day 15 GC, Week 3 is from the day after Day 15 GC to Day 21. The number of days for Week 2 and Week 3 maybe equal to, less than, or greater than 7. See Section [5.3.2](#) for the details. The weekly average score is the weekly sum score divided by the number of days with non-missing in that week. If daily scores are missing for more than half of total days in a specific week, the average score is missing for that week.
- Change from baseline at each timepoint = observed (or derived as described above) value at each timepoint – baseline.
- The observed value and the change in PGIS

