5.3.2. CDSD

The weekly average score of each severity item and frequency question of CDSD (Diarrhea, Abdominal Pain, Bloating, Nausea, Number of times Vomiting, Tiredness, Number of Bowel Movements and Number of events of Diarrhea) as well as the weekly average CDSD Total Score, weekly average CDSD GI Domain Score (see [Section 2.3](#) and [Appendix 2.2](#)) and change from baseline will be descriptively summarized as stated in Section 5 for each treatment group by timepoint.

The change from baseline for weekly average of each of the 5 severity items and 3 frequency questions, the weekly average CDSD Total Score, and the weekly average CDSD GI Domain Score will be analyzed using ANCOVA models in [Section 4.2.1](#) by timepoint. LSM of the treatments with 95% CI, LSM of the treatment difference with PBO, p-value and 95% CI will be generated.

If there are multiple records on a same day, the earliest one will be used for analysis.

The analysis set(s) used for these endpoints are found in Section [5](#).

Weekly Time Definitions:

	Regardless the day of Day 15 GC	Day 15 GC is at day 14	Day 15 GC is at day 15	Day 15 GC is at day 16	Day 15 GC is at day 17
Baseline	Day -7 to -1				
Week 1	Day 1 to 7				
Week 2		Day 8 to 13	Day 8 to 14	Day 8 to 15	Day 8 to 16
Week 3		Day 14 to 21	Day 15 to 21	Day 16 to 21	Day 17 to 21
Week 4	Day 22 to 28				
Week 5	Day 29 to 35				
Week 6	Day 36 to 42				

In addition, the change from baseline in CDSD Nausea score and vomiting frequency for Day 15, 3-day average and 7-day average (weekly average) score, will be summarized as stated above, and analyzed within placebo and KAN treatment, evaluating the paired difference from baseline using the Wilcoxon Signed-rank test. The Mann-Whitney U test (Wilcoxon Rank Sum test) will be used to test the difference in the change from baseline for placebo vs KAN-101. The median difference between treatment groups estimated by the Hodges–Lehmann method along with the 95% CI will be reported as well.

Line plots by treatment group will be provided for LSM 95% CI).

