Table 7 Analysis Windows for biopsy endpoints (Vh:Cd ratio, IEL density, Marsh-Oberhuber score)

Visit Label	Targeted Day	Analysis window for data sets
Baseline (Screening up to first dosing)	Day 1 pre-dosing	Last observation prior to first dosing date
Day 29	Day 29	Day 22 – Day 43

Table 8 Analysis Windows for IL-2 and CDSD at Day 15 (first GC Day)

Visit Label	Targeted Day	Analysis window for data sets
Day 15	Day 15	The first GC day, Day 14 – Day 17

[figure not shown]

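### SAP 2.3 and the SAP 5.3.2 table disagree on whether CDSD Week 3 includes the first gluten-challenge day; separately, fixed Weeks 4 and 5 can misplace 1 or 2 days when the challenge does not start on Day 15

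*SAP*

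**What the plan says.** SAP 2.3 gives two rules that meet at the first challenge day: "Week 2 is from Day 8 to the day before Day 15 GC", and "Week 3 is from the day after Day 15 GC to Day 21". It adds that "The number of days for Week 2 and Week 3 maybe equal to, less than, or greater than 7" and refers to SAP 5.3.2 for details. A weekly average is the sum over non-missing days divided by their number. It is set to missing when more than half of the week's days have no score.

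The Weekly Time Definitions table in SAP 5.3.2 starts Week 3 on the first GC day itself: Days 14–21, 15–21, 16–21 or 17–21 for starts on Day 14, 15, 16 or 17. Week 4 (Days 22–28), Week 5 (Days 29–35) and Week 6 (Days 36–42) stand in the column "Regardless the day of Day 15 GC". SAP Appendix 2.1, Table 8, sets the allowed start: "The first GC day, Day 14 – Day 17".

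On the length of the challenge, Protocol 8.2.1 says "Compliance with the GC is defined as completion of all 14 days of the GC" and sends materials home for 13 days after the clinic dose. Protocol 4.1 and Table 1 describe the challenge as running through Day 28. Neither document says what happens to Day 28 when the start moves.

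**The concern.** Weekly CDSD changes from baseline are compared between arms by ANCOVA, with p-values, at each timepoint. The related protocol objective concerns symptoms before and during the challenge. Two programmers following the two SAP sections would build different Week 3 datasets. The disputed day is the supervised one, on which participants are observed for at least 4 hours for acute reactions, so it is not an arbitrary day to keep or drop.

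The second matter is that the start of the challenge may move by up to two days while the boundaries after Day 21 do not. Some participants could then have gluten-free days in an on-challenge week, or gluten days in the week after it.

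**Working it through.** The plan states no figure to reproduce; the check is a count of days.

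**Inputs.** First GC day s = 14, 15, 16 or 17 (SAP Table 8); 14 consecutive daily doses, so gluten days run from s to s + 13 (Protocol 8.2.1); week windows from SAP 2.3 and 5.3.2.

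**Week lengths.** Week 2 = s − 8 days under both sections. Week 3 = 22 − s days by the table and 21 − s by the text.

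**Gluten days / days in window**

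| First GC day | GC runs | Week 2 | Week 3, table | Week 3, text | Week 4 | Week 5 | Week 6 |
|---|---|---|---|---|---|---|---|
| 14 | 14–27 | 0/6 | 8/8 | 7/7 | 6/7 | 0/7 | 0/7 |
| 15 | 15–28 | 0/7 | 7/7 | 6/6 | 7/7 | 0/7 | 0/7 |
| 16 | 16–29 | 0/8 | 6/6 | 5/5 | 7/7 | 1/7 | 0/7 |
| 17 | 17–30 | 0/9 | 5/5 | 4/4 | 7/7 | 2/7 | 0/7 |

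By the table, the gluten days in Weeks 3 to 5 add to 14 for every start (for Day 17, 5 + 7 + 2). By the text they add to 13, because the first day is in no week.

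**If dosing stops at Day 28 for late starters.** Week 5 becomes 0/7 for Day 16 and Day 17 starts. The Day 14 row is unchanged.

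**Effect on the Week 3 average.** Let L be the table length, x the first-day score and m the mean of the other L − 1 days, with a complete diary. The table gives ((L − 1)m + x)/L = m + (x − m)/L; the text gives m. The difference is (x − m)/L: one-eighth, one-seventh, one-sixth or one-fifth of the gap x − m for starts on Days 14, 15, 16 and 17. The documents give no daily CDSD scores, so the gap itself cannot be sized.

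**Effect on the missing-day rule.** With L days, up to L/2 (rounded down) may be missing.

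| First GC day | Table: may be missing / must be present | Text: may be missing / must be present |
|---|---|---|
| 14 | 4 / 4 of 8 | 3 / 4 of 7 |
| 15 | 3 / 4 of 7 | 3 / 3 of 6 |
| 16 | 3 / 3 of 6 | 2 / 3 of 5 |
| 17 | 2 / 3 of 5 | 2 / 2 of 4 |

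One of the two limits changes in every row.

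**The case against.** SAP 2.3 defers to 5.3.2 for details. Its remark that Week 3 may exceed 7 days fits only the table, since the 2.3 rule gives at most 7. The intended rule can therefore be inferred. For nausea and vomiting, Day 15 is also analysed on its own and the 3-day averages start from the first GC day, so that day is not lost for those items. Any rule applies equally to both blinded arms. Appendix 2.2, cited for the calculation, is withheld as copyrighted and might say more. CDSD is exploratory, and Protocol 9.4.4 says that such results may not be described in the study report. All of this stands and keeps the point small. It does not remove a derivation rule in 2.3 that says the opposite of the table.

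A reader might also infer that the last SAP version re-anchored other windows and left the diary behind, because it records that the PGIS, PGIC, vital-sign and laboratory windows "were updated to relative to the first (or second) GC day instead of absolute study day". The documents do not support that. The same version added the diary's Week 2 and Week 3 definitions for a Day 17 start and widened Table 8. The re-anchored windows also keep a fixed tail, with Day 29 ending on Day 35 and Day 42 starting on Day 36.

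**Conclusion.** The conflict between 2.3 and 5.3.2 is real and touches every start day, including Day 15. Week 3 has 4 to 7 days by one rule and 5 to 8 by the other, and both its average and its missing-day limits depend on which is used.

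The fixed later weeks are a separate and narrower matter. Week 4 has 1 gluten-free day of 7 for a Day 14 start. Week 5 has 1 or 2 gluten days of 7 for a Day 16 or 17 start. These counts assume 14 consecutive doses without gaps.

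Two stronger readings should be resisted. A reader might infer that the Week 3 conflict itself mixes gluten and gluten-free days; it does not, because Week 3 is wholly on gluten and Week 2 wholly off it under either rule. A reader might also quote 2/7 (29%) of Week 5 as on gluten. That is the worst case, for a Day 17 start, and holds only if dosing continues to Day 30, which the documents leave unsettled. The share of participants starting off Day 15 is not given, so no effect on the arm comparison can be estimated. The primary and secondary analyses are unaffected.

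**What to change.** Correct SAP 2.3 so that Week 3 starts on the first GC day, as in the 5.3.2 table. Then derive the later weeks from that day: Week 3 = GC days 1–7, Week 4 = GC days 8–14, Week 5 = the next 7 days, Week 6 = the remaining days to Day 42.

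The cost is SAP wording and one date derivation, with no new data. Week 6 becomes 42 − (s + 20) = 22 − s days: 8, 7, 6 or 5 for starts on Days 14 to 17. Weeks 5 and 6 also lose their alignment with the Day 35/36 cut in Appendix 2.1 for starts other than Day 15.

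The passages on 14 challenge days and on Day 28 should be reconciled for late starters at the same time. If such participants stop at Day 28, the re-anchored Week 4 (Days 23–29 or 24–30) would itself hold 1 or 2 days without gluten.

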3. ANALYSIS SETS

For purposes of analysis, the following analysis sets are defined:

Analysis Set	Description
Enrolled	All participants who sign the ICD.
Biomarker Analysis Set (BAS)	All participants who are randomly assigned to study intervention, receive any portion of study intervention, and have completed the GC on Day 15, without prohibited medications. Participants will be analyzed according to the intervention they are randomized.
Full analysis set (FAS)	All participants who are randomly assigned to study intervention, receive all 3 doses of study intervention, and complete at least 7 days of the 2-week GC without prohibited medications. Participants will be analyzed according to the intervention they are randomized.

Analysis Set	Description
Per protocol set (PPS)	The PPS will include all participants from the FAS who complete all 14 days of the 2-week GC and biopsies, and without major protocol violations that might affect the evaluation of the effect of study intervention on the primary endpoint. The PPS will be used in sensitivity analyses of the primary and secondary endpoints. Specific reasons for warranting exclusion from this population will be documented prior to database lock.
Safety analysis set (SAS)	All participants who receive any portion of study intervention. Participants will be analyzed according to the intervention they actually received.
PK analysis set (PKAS)	All participants who receive any portion of study intervention and have at least one concentration value.

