5. ANALYSES AND SUMMARIES

In general, observed values and change from baseline (where applicable) will be descriptively summarized by treatment group with number of observations, mean, SD, min, 1st, 2nd (median) and 3rd quartiles, and max, unless otherwise specified. For log-transformed values the geometric mean and 95% CI will be presented with the summary statistics.

Data will be summarized and analyzed by treatment group for the main population of interest and a separate sensitivity/supplementary analysis(ses) based on the chosen analysis set from Section 3).

Endpoint	Analysis Set Applied for Main Analysis	Analysis Set Applied for Sensitivity/Supplementary Analysis
Biopsy (Vh:Cd, IEL Density Marsh-Oberhuber Score)	Full Analysis Set	Per Protocol Set and Safety Analysis Set
Biomarker (IL2)	Biomarker Analysis Set	Per Protocol Set and Safety Analysis Set
PK	PK Analysis Set	N/A
PRO (CDS, PGIS, PGIC)	Full Analysis Set	N/A
Demography and Safety	Safety Analysis Set	N/A
ADA	Safety Analysis Set	N/A

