7. CHANGES FROM PROTOCOL

- Sample size calculation was updated to include consideration for multiple looks. Decision rules were also updated.
- Sensitivity/Supplementary analyses were updated with the new populations.

- Prohibited medications are considered in the study set definitions with the other intercurrent events (noncompliance with study medications and noncompliance with gluten challenge).
- An additional study set was added for IL2 called the BAS.

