Appendix 1. Summary of Efficacy/Exploratory Analyses

Endpoint	Analysis Type	Population	Analysis Model
Change from baseline in Vh:Cd ratio at Day 29	Summary	FAS	N/A
	Main analysis	FAS	ANCOVA with terms treatment, baseline
	Sensitivity/supplementary analysis	PPS, SAS	ANCOVA with terms treatment, baseline
GC IL-2 (log-transformed) change from Day 15 pre-GC to Day 15 post GC	Summary	BAS	N/A
	Analysis	BAS	ANCOVA with terms treatment, baseline
	Sensitivity/supplementary analysis	PPS, SAS	ANCOVA with terms treatment, baseline
Changes from baseline in IEL density in duodenum biopsy after 2-week GC (at Day 29)	Summary	FAS	N/A
	Analysis	FAS	ANCOVA with terms treatment, baseline
	Sensitivity/supplementary analysis	PPS, SAS	ANCOVA with terms treatment, baseline

Endpoint	Analysis Type	Population	Analysis Model
CDSD change from baseline at each timepoint	Summary	FAS	N/A
	Analysis	FAS	ANCOVA with terms treatment, baseline
	Sensitivity/supplementary analysis	PPS, SAS	ANCOVA with terms treatment, baseline
CDSD 1-Day, 3-Day, 7-Day Nausea Score and Vomiting Frequency and change from baseline at each timepoint post-gluten challenge	Summary	FAS	Observed cases
	Analysis	FAS	All data collected will be included regardless of intercurrent events. Missing data will not be imputed. Wilcoxon Signed-rank test for change from baseline within each group
	Analysis	FAS	All data collected will be included regardless of intercurrent events. Missing data will not be imputed. Mann-Whitney U test (Wilcoxon)

Endpoint	Analysis Type	Population	Analysis Model
			Rank Sum test) for comparison of placebo vs KAN group for change from baseline
PGIS change from baseline at each timepoint	Summary	FAS	N/A
	Analysis	FAS	ANCOVA with terms treatment, baseline
PGIC at each timepoint	Summary	FAS	N/A
	Analysis	FAS	ANOVA with term treatment
Marsh- Oberhuber score	Summary	FAS, PPS, SAS	N/A

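### The Day 15 nausea and vomiting tests use the FAS, whose membership is settled by later gluten-challenge days; the Week 3 start and the CDSD sensitivity sets are also stated inconsistently (minor, exploratory)

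*SAP*

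**What the plan says.** **Endpoint and tests.** SAP 2.3 and 5.3.2 include a single-day Day 15 value (the first GC day) among the nausea and vomiting outcomes. SAP 5.3.2 names "the change from baseline in CDSD Nausea score and vomiting frequency for Day 15, 3-day average and 7-day average (weekly average) score". Change from baseline gets a signed-rank test within arm, a rank-sum test between arms, and a Hodges–Lehmann difference with its interval.

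**Analysis set.** SAP 5.3.2 states "The analysis set(s) used for these endpoints are found in Section" 5. There the row beginning "PRO (CDS, PGIS, PGIC" gives the FAS as the main set and N/A for sensitivity sets. Appendix 1 also gives the FAS for "CDSD 1-Day, 3-Day, 7-Day Nausea Score and Vomiting Frequency and change from baseline at each timepoint post-gluten challenge", and both of its test cells add "All data collected will be included regardless of intercurrent events". In SAP 3 the FAS needs all three doses and participants who "complete at least 7 days of the 2-week GC without prohibited medications". SAP 7 says prohibited medication is handled in the set definitions with the other intercurrent events, listed as "noncompliance with study medications and noncompliance with gluten challenge".

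**The other Day 15 endpoint.** IL-2 uses the Biomarker Analysis Set, for those who "receive any portion of study intervention, and have completed the GC on Day 15, without prohibited medications". It does not depend on later GC days.

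**Week 3.** SAP 2.3 ends Week 2 the day before the first GC and begins Week 3 the day after it. The weekly table in 5.3.2 begins Week 3 on the GC day in all four of its columns (GC on Day 14, 15, 16 or 17).

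**Sensitivity sets.** For the general CDSD analysis (ANCOVA), Appendix 1 lists PPS and SAS, against N/A in Section 5.

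**The concern.** A symptom score recorded on Day 15 is kept or discarded according to what the participant does over roughly the following week, and that may be a consequence of the score. This is selection on a post-outcome event. If the participants with the worst reactions stop gluten early, and more of them do so in one arm, the arms left in the FAS no longer compare like with like at Day 15. If stopping is unrelated to the reaction, the only cost is a smaller sample.

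The Week 3 conflict leaves the first, supervised GC day in no week under one rule and in Week 3 under the other. That can change both the weekly average and whether an average exists. The disagreement on sensitivity sets leaves it open whether early stoppers appear in any weekly CDSD analysis.

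**Working it through.** **1. The plan's only figure on arm-specific loss.** Protocol 9.6 gives 82% power if 20% of KAN-101 and 40% of placebo participants lack the primary endpoint. Inputs: difference 0.5, SD 0.5, 26 per arm, two-sided 5%. Evaluable: 26 × 0.8 = 20.8 and 26 × 0.6 = 15.6. The t-test noncentrality is 0.5 / (0.5 × √(1/n₁ + 1/n₂)). With 21 and 15 it is 2.96 and power is 82.0%; with 21 and 16 it is 3.01 and power is 83.4%. The figure reproduces. It implies about 5 and 10 participants lost. For Day 15 this is only a guide on the high side, because some loss may precede Day 15.

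**2. When FAS membership is settled.** Earliest seventh GC day = start + 6: Day 20, 21, 22 or 23 for a start on Day 14, 15, 16 or 17. With a Day 15 start, the first two 3-day windows (Days 15–17 and 18–20) also close before Day 21, so they share the issue.

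**3. Size of the selection effect (all inputs assumed).** The Day 15 score has five levels, with placebo at 35/20/20/15/10%, and baseline is the same for all. The latent KAN-101 score is shifted by 0.5 SD toward fewer symptoms. Stopping is the upper tail of a normal variable with correlation ρ to the participant's Day 15 latent score. Vomiting counts are not modelled. The index is P(placebo worse) + ½P(tie). In all GC starters it is 0.62. In the FAS it is:

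| Stopping, KAN-101 / placebo | ρ = 0 | ρ = 0.3 | ρ = 0.5 |
|---|---|---|---|
| 10% / 25% | 0.62 | 0.60 | 0.59 |
| 20% / 40% | 0.62 | 0.60 | 0.58 |
| 25% / 10% | 0.62 | 0.64 | 0.65 |
| 40% / 20% | 0.62 | 0.64 | 0.66 |
| 20% / 20% or 30% / 30% | 0.62 | 0.62 | 0.62 |

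With no true difference (0.50), the FAS gives 0.46 to 0.48 when placebo stops more and 0.52 to 0.54 when KAN-101 stops more, at ρ = 0.3 and 0.5.

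Rank-sum power with 26 starters per arm is about 35%. In the FAS at ρ = 0.3 or 0.5 with unequal stopping it runs from about 15% to 44%.

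A second assumed model has no drug effect, fixed 20%/40% loss, and the log-weight of loss rising per score point by 0, 0.5, 1 or 2. The two-sided 5% rank-sum test then rejects in 4.5%, 8.8%, 14.4% and 20.7% of runs in the FAS. With all 26 per arm it rejects in 4.4% to 5.2%.

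**4. Week 3.** Length is 22 − start (5.3.2 table) or 21 − start (SAP 2.3). The example has nausea 3 on the GC day and 1 on every other day.

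| First GC on | Days, table | Days, 2.3 | Average, table | Average, 2.3 |
|---|---|---|---|---|
| Day 14 | 8 | 7 | (3+7)/8 = 1.25 | 1.00 |
| Day 15 | 7 | 6 | (3+6)/7 = 1.29 | 1.00 |
| Day 16 | 6 | 5 | (3+5)/6 = 1.33 | 1.00 |
| Day 17 | 5 | 4 | (3+4)/5 = 1.40 | 1.00 |

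SAP 2.3 sets the weekly average to missing when more than half the days are missing. The two rules can disagree on this in either direction:
- GC on Day 15, that day and three others missing: 4 of 7 missing under the table (no score), 3 of 6 under 2.3 (score).
- GC on Day 16, that day present and three others missing: 3 of 6 under the table (score), 3 of 5 under 2.3 (no score).

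**The case against.** **A reader might infer that the Appendix 1 row contradicts itself**, since it names a set built by excluding intercurrent events and then says all data are included whatever those events. The documents do not support that. Protocol 8.2.1 defines GC compliance as completing all 14 days, while the FAS needs only 7. Participants with 7 to 13 GC days are noncompliant yet in the FAS, and the phrase can mean that none of their data are dropped. The wording is unclear rather than contradictory.

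**A reader might also infer a bias in favour of KAN-101**, because Protocol 2.2.3 reports more participants with GI adverse events on drug than on placebo in the first-in-human study. That passage does not say whether those events followed dosing or gluten, and says nothing about stopping gluten. It also reports no meaningful safety differences among treatment groups. The only arm-specific loss in the documents, the Protocol 9.6 example, is higher on placebo. If both arms stop at one common symptom threshold in the model above, KAN-101 stops less (18% to 20% against 25%, or 31% to 34% against 40%). The FAS index is then 0.60 to 0.615, a small shift toward no effect. The direction stays open.

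**One set for every window is a defensible choice**, because it keeps the same participants throughout, and Section 5 and Appendix 1 agree on it. The IL-2 set is not a clean alternative. Its prohibited-medication condition has no time limit, and GC completion under Protocol 8.2.1 means eating the whole portion within about 15 minutes, so someone too nauseated to finish would leave it. This argues for showing a second Day 15 result, not for replacing the FAS.

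**Week 3 is largely editorial.** SAP 2.3 refers to 5.3.2 for details, so the table probably governs. Appendix 2.2, also cited for the calculation, is withheld and could not be checked.

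What stands: the Day 15 set depends on later events, two Week 3 rules are in the text, and the sensitivity sets disagree.

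**Conclusion.** The point holds as a minor one. The textual parts are certain: the Day 15 comparison uses a set settled on Day 21 at the earliest when GC starts on Day 15, Week 3 differs by exactly one day (the first GC day), and Section 5 and Appendix 1 list different CDSD sensitivity sets.

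The bias is conditional. It needs stopping that is related to the Day 15 reaction and that differs by arm. The documents give neither the rates nor the relation, so the range of 0.58 to 0.66 around a true 0.62 illustrates possible size and predicts nothing.

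Consequences are limited. Protocol 9.4.4 makes these endpoints exploratory and says they may be left out of the CSR. GC symptoms are also recorded as adverse events and summarised in the safety set (Protocol 8.2.1, SAP 5.5.1). At about 35% power under the assumed effect, the Day 15 test decides little. The primary analysis and its power are unaffected.

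**What to change.** (a) In SAP 5, 5.3.2 and Appendix 1, add a Day 15 nausea and vomiting analysis in all randomised participants who started the Day 15 GC, analysed as randomised, with no condition on later GC days or later medication. Show it beside the FAS result. State what "All data collected will be included regardless of intercurrent events" means within the FAS.

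State also that the first 3-day windows share the selection issue, and keep the FAS as their main set. Any all-starters result there should be supplementary and labelled as including days off gluten, because it is not clearly better. At ρ = 0.5 with 10%/25% and 20%/40% stopping, all starters give 0.579 and 0.564 if stoppers' scores fall two levels off gluten, against 0.593 and 0.584 in the FAS. With a one-level fall they give 0.603 and 0.596.

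(b) In SAP 2.3, start Week 3 on the first GC day, as in the 5.3.2 table.

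(c) Make Section 5 and Appendix 1 list the same CDSD sensitivity sets.

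Cost: SAP wording and one extra set of Day 15 tables. The diary data are already collected, and no main set changes.
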